The protocol, informed consent form(s), recruitment materials, and all participant materials will be submitted to the Institutional Review Board (IRB) for review and approval. Approval of both the protocol and the consent form must be obtained before any participant is enrolled. Any amendment to the protocol will require review and approval by the IRB before the changes are implemented to the study. In addition, all changes to the consent form will be IRB-approved; a determination will be made regarding whether a new consent needs to be obtained from participants who provided consent, using a previously approved consent form.]

[figure not shown]
1 PROTOCOL SUMMARY

1.1 SYNOPSIS

Title:	Phase 1/2 Trial of Indomethacin in Chronic Pancreatitis (The PAIR Trial)
Study Description:	Chronic pancreatitis (CP) is a disabling disease that causes chronic pain, diabetes and malnutrition, and for which there is no effective, disease-modifying medical therapy. Preliminary studies suggest that widely available anti-inflammatory drugs such as indomethacin, which decrease prostaglandin E2 (PGE ₂) production, could be repurposed to lessen the severity of CP. In this prospective, randomized, placebo-controlled study, indomethacin or placebo will be given to patients with CP, and pancreas juice PGE ₂ levels will be measured, in order to determine whether standard doses of indomethacin effectively suppress pancreatic PGE ₂ production and would be suitable for large scale, multicenter trials, with the goal of improving pain and quality of life in patients with this chronic illness.
Objectives:	
Primary Objective: to assess the physiologic effect of orally administered indomethacin (IN) on pancreatic juice PGE₂ concentrations in patients with chronic pancreatitis (CP).
 
Secondary Objectives: A) To correlate drug-induced changes in pancreatic juice PGE₂ levels with changes in salivary and blood PGE₂ levels, blood IN levels, and changes in patient-reported pain outcome (PRO) and quality of life (QOL), and B) to establish a basis for subsequent multicenter clinical trials of chronic COX-2 inhibition in CP.

Specific Aims:	1. To obtain steady-state pharmacologic data assessing the magnitude and variability of change in pancreas juice, blood, and saliva PGE ₂ concentrations after administration of oral IN or placebo to CP patients for 28 days. 2. To correlate changes in pancreas juice PGE ₂ concentrations with changes in PRO and QOL after 28 days of study drug administration. Endpoints:
	Primary Endpoint: Decrease in mean pancreatic juice PGE ₂ concentration after indomethacin treatment, to no more than 66% of baseline, and statistically significant in comparison to placebo. Secondary Endpoints: Correlation of pancreatic juice, blood, and saliva PGE ₂ levels; correlation of post-treatment decreases in pancreas juice PGE ₂ concentrations with improvements in patient-reported outcomes (pain and quality of life).
Study Population:	32 persons with chronic pancreatitis of any gender, ≥ 18 years and ≤ 70 years of age, who are receiving care at Mayo Clinic Rochester or Ohio State University and are undergoing clinically indicated upper GI endoscopy (EGD) or endoscopic ultrasound (EUS).
Phase:	1/2
Description of Sites/Facilities Enrolling Participants:	Mayo Clinic Rochester and Ohio State University.
Description of Study Intervention:	Indomethacin 50 mg po BID vs placebo po BID for 28 days.
Study Duration:	2 years.
Participant Duration:	Up to 3 months.

1.2 SCHEMA

1.3 SCHEDULE OF ACTIVITIES (SOA)

Procedures	Screening Day -28 to 0	Study Visit 1 Day -28 to 0	Study Visit 2 Day 0	Phone Call A Day 7	Phone Call B Day 14	Phone Call C Day 21	Study Visit 3 Day 25 - 28	Phone Call D Day 56 - 58
Review inclusion/exclusion criteria	X							
Informed consent	X							
Demographics		X						
Medical history		X						
Medications (documented)		X					X	
BPI, PROMIS-10 completed		X					X	
List of NSAIDS to avoid given to participant		X						
Vital signs including height, weight		X						
Physical Exam documented		X						
Blood collection and processing, including serum creatinine if not already checked within 30 days		X					X	
Saliva collection and processing		X					X	
Pregnancy test ^a			X				X	
Randomization			X					
GI Endoscopy			X				X	
Pancreas juice collection and processing			X				X	
Dispense study medication			X					
Interim history form (telephone interview)				X	X	X		X
Daily medication and pain diary				X-----X				
Collect unused study medication and document							X	
Complete Case Report Forms (CRFs)	X	X	X	X	X	X	X	X

^a Urine pregnancy test within 48 hours prior to GI endoscopy, in women of childbearing potential.

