8.2 SAFETY AND OTHER ASSESSMENTS

Screening of potential participants for eligibility will be done during the screening visit. Additional elements (serum creatinine result, presence of active GI ulceration) will be determined subsequent to the screening visit when laboratory results are available, and during the baseline endoscopy.

Physical Examination, including chest, cardiac, and abdominal exams, will be documented in the patient's medical record within 30 days of their baseline endoscopy procedure.

Height and weight will be measured within 30 days of the participant's baseline endoscopy procedure.

Serum creatinine will be measured within 30 days of the participant's baseline endoscopy procedure. This test will be performed for research purposes, and the result placed in the patient's medical record, if it is not being performed clinically. Participants with serum creatinine outside of the laboratory normal range will be withdrawn from the study and considered non-accrued.

Blood draw will be up to 30 cc at study visit 1 (baseline) and up to 20 cc at study visit 3 (day 28). This includes up to 10 cc for measurement of serum PGE2 at both time points. Baseline blood draw also includes up to 10 cc for measurement of serum creatinine if not already measured for clinical purposes, and up to 10 cc for aspirin and NSAID screens. Day 28 blood draw also includes up to 10 cc for indomethacin level. Details of biospecimen handling are documented in the study biospecimen SOP.

Endoscopic procedures will be performed on clinical GI Endoscopy Units at the current standard of clinical care at Mayo Clinic Rochester and Ohio State University, including the use of monitored anesthesia care (MAC) or general anesthesia (GA) at the discretion of the attending gastroenterologist and anesthesiologist. Participants will receive pre-procedure evaluation, intra-procedural monitoring, and post-procedural recovery care identical to that provided to patients undergoing endoscopy in these units. Staff nurses, anesthetists, and GI endoscopists will be available to assess symptoms and adverse events and provide appropriate treatment during endoscopic procedures and their recovery period. Participants will be discharged from the endoscopy unit when they meet the unit's standard discharge criteria.

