9 STATISTICAL CONSIDERATIONS

9.1 STATISTICAL HYPOTHESES

Primary Endpoint:

- Decrease in mean pancreatic juice PGE₂ concentration after indomethacin treatment, to no more than 66% of baseline, and statistically significant in comparison to placebo.

Secondary Efficacy Endpoints:

- Changes in salivary and blood PGE₂ concentrations after study drug administration will have statistically significant correlation with changes in PJ PGE₂ concentrations and blood IN levels.
- Salivary and blood PGE₂ concentrations will have statistically significant correlation with PJ PGE₂ concentrations.
- Improvement in pain and quality of life of study participants will have statistically significant correlation with post-treatment changes in PJ PGE₂ concentrations.
- Exploratory analysis of molecular analytes (cytokine and microbiome) in blood and saliva will be done to measure effect of IN administration.

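### Baseline saliva, blood and questionnaires may precede baseline pancreatic juice by up to 28 days, which can weaken the baseline-level and change-score correlations

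*Combined protocol and SAP*

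**What the plan says.** The Schedule of Activities (section 1.3) sets the timing:

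- "Saliva collection and processing" and "BPI, PROMIS-10 completed" are each marked at "Study Visit 1 Day -28 to 0" and at "Study Visit 3 Day 25 - 28", with nothing at Visit 2. Blood follows the same pattern, and section 8.2 confirms that the PGE2 draws belong to Visits 1 and 3.
- "Pancreas juice collection and processing" is marked at "Study Visit 2 Day 0" and at Visit 3, with nothing at Visit 1.
- Section 6.4 has the follow-up blood drawn on the morning of the follow-up endoscopy.

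The correlations that use these pairs are secondary endpoints (sections 1.1 and 3). Section 9.1 states one of them as "Salivary and blood PGE₂ concentrations will have statistically significant correlation with PJ PGE₂ concentrations". Two others concern changes: saliva and blood PGE2 against juice PGE2, and pain and quality of life against juice PGE2. Section 2.2 gives the purpose: a high correlation might let non-invasive specimens stand in for juice in later studies.

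Section 4.1 (Methods) reads differently. It describes a single baseline collection that includes juice and allows up to 4 weeks between it and the first day of drug. Sections 1.3 and 6.3 put juice, allocation and dispensing together on Day 0.

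**The concern.** A correlation between two fluids, or between a fluid and a symptom score, is most informative when both are measured at the same time. Here the follow-up pair is synchronous and the baseline pair need not be. The gap may differ between participants, and no section limits it below 28 days or allows for it in the analysis. Section 9.4.3 treats baseline as one time point for juice PGE2 and the patient-reported scores.

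The aspirin/NSAID rule adds to this. Sections 5.2 and 6.5 tie the 7-day aspirin- and NSAID-free period to the baseline endoscopy, not to Visit 1. The list of drugs to avoid is first handed out at Visit 1, the blood for the aspirin/NSAID screen is part of that draw (section 8.2), and use up to once a week is eligible. Visit 1 blood and saliva can therefore be taken before the drug-free period begins, while juice is taken after it.

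At stake are the baseline-level and change-score evidence on non-invasive markers, and the pilot estimates linking juice PGE2 to pain and quality of life.

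**Working it through.** The plan gives no target correlation, precision or power for these endpoints, so there is no stated figure to reproduce.

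**Timing, from the Schedule's windows**

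- Baseline gap between juice and the other measures: 0 − 0 = 0 days to 0 − (−28) = 28 days.
- Interval for change in juice: Day 0 to Day 25–28, so 25 to 28 days.
- Interval for change in saliva, blood, BPI and PROMIS-10: 25 − 0 = 25 days to 28 − (−28) = 56 days.

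**Attenuation of the baseline-level correlation (illustration)**

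Assumed, not in the documents: same-day correlation r = 0.60, and within-person autocorrelation a of 0.7 or 0.5 at 28 days, decaying exponentially. From the plan: n = 32 (16 per arm, section 9.2). Test: Fisher z, two-sided 0.05, with

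power ≈ Φ(atanh(r)·√(n − 3) − 1.96), √29 = 5.385.

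Same day: atanh(0.60) = 0.693; 0.693 × 5.385 = 3.733; Φ(1.773) = 0.96.

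For gaps uniform over 0–28 days, the mean autocorrelation is (1 − a)/(−ln a): 0.3/0.357 = 0.841 for a = 0.7, and 0.5/0.693 = 0.721 for a = 0.5.

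| Scenario (a = 0.7 / 0.5) | Factor | Correlation | Power |
|---|---|---|---|
| Same day | 1 | 0.60 | 0.96 |
| Gaps uniform over 0–28 days, no stable part | 0.84 / 0.72 | 0.50 / 0.43 | 0.85 / 0.70 |
| All at 28 days, half of covariance stable: 0.5 + 0.5a | 0.85 / 0.75 | 0.51 / 0.45 | 0.86 / 0.74 |
| All at 28 days, no stable part: a | 0.70 / 0.50 | 0.42 / 0.30 | 0.67 / 0.38 |

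The smallest correlation detectable with 80% power at n = 32 is about 0.48, so there is little room for avoidable attenuation.

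**Attenuation of the change-score correlation (illustration)**

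Let a(t) = 0.5^(t/half-life), gap g and 28 days between juice samples. For the fluctuating part, the factor on r is

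[1 − a(28+g) − a(28) + a(g)] / [2√((1 − a(28))(1 − a(28+g)))].

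Example, half-life 14 days and g = 14: (1 − 0.125 − 0.25 + 0.5) / (2√(0.75 × 0.875)) = 1.125/1.620 = 0.69.

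Over assumed half-lives of 3 to 56 days the factor is 0.60–0.88 for a 7-day gap, 0.52–0.78 for 14 days and 0.50–0.65 for 28 days. With an assumed same-day change correlation of 0.50, power is 0.84; a factor of 0.75 gives 0.375 and power 0.57; a factor of 0.50 gives 0.25 and power 0.28.

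A treatment effect shared by both measures softens this. With an assumed 1 SD shift in both and a(28) near 0, the correlation is (r(1 + a(g)) + 0.25)/2.25. For r = 0.50 this falls from 1.25/2.25 = 0.56 with no gap to 0.75/2.25 = 0.33 at worst, rather than from 0.50 to 0.25.

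**The case against.** The strongest reply is about size and reach, and much of it stands.

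- Twenty-eight days is a maximum. Visit 1 may fall on Day 0, and the documents give no distribution of gaps. A reader might infer that every baseline pair is four weeks apart; the window does not say so.
- Stable differences between patients survive a gap. If the whole association is stable, a level correlation loses nothing.
- A reader might infer that the trial could not judge whether saliva or blood can replace juice, or that a usable marker would be dropped. The documents do not support that. Visit 3 supplies same-visit juice, blood and saliva in both arms, and the level hypothesis in section 9.1 is not confined to baseline.
- Section 4.1 acknowledges milder fluctuations in pancreatic inflammation, but it does not say how far saliva or blood PGE2 varies over four weeks. Hospitalization for acute pancreatitis in the 6 weeks before enrollment is excluded, and during participation it leads to withdrawal (section 5.2), which removes some larger swings.
- Section 9.4.9 declares the pain and quality-of-life analyses exploratory. Sections 4.1 and 8.1 also describe a pain diary kept at baseline, although the Schedule marks it only after Day 0.

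One reply does not stand. On section 4.1's wording, blood, saliva and juice form one baseline collection, but the Schedule and section 8.2 assign them to different visits, and nothing requires those visits to coincide. That is a conflict to settle, not a safeguard.

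**Conclusion.** The point holds as a modest, avoidable loss of efficiency. The timing mismatch follows directly from the Schedule. It can weaken the baseline-level and change-score correlations of juice PGE2 with saliva and blood PGE2, and with pain and quality of life.

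The size cannot be derived from the documents. Under the assumptions above, the baseline-level correlation runs from no loss (coincident visits or a fully stable association), through about 0.50 or 0.43 in place of 0.60 (uniform gaps), to 0.42 or 0.30 in the worst case. The worst case needs everyone at 28 days and no stable between-patient association, so it is a bound and not an expectation.

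A reader might also infer that the primary result is compromised. It is not: juice PGE2 is compared between Day 0 and Visit 3, and neither sample depends on Visit 1. The same-visit correlations at Visit 3 are untouched too.

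**What to change.** 1. Collect, or repeat, baseline saliva, PGE2 blood, BPI and PROMIS-10 at Visit 2 (Day 0) before sedation and secretin, mirroring Visit 3. Keep the eligibility creatinine at Visit 1. This also puts the PGE2 specimens after the 7-day aspirin/NSAID-free period.
2. Where a same-day sample is not obtained, record the gap in days and prespecify a sensitivity analysis restricted to short gaps.
3. Reconcile section 4.1 (one baseline collection including juice, up to 4 weeks before drug) with sections 1.3 and 6.3 (juice, allocation and dispensing on Day 0).

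The cost is a revised Schedule, a slightly longer Day 0 visit and possibly a second blood draw. Participants already attend that day for endoscopy.

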2 INTRODUCTION

2.1 STUDY RATIONALE

Chronic pancreatitis (CP) is a chronic fibro-inflammatory disease. There is no medical therapy that modifies the disease course of CP. Our **long-term goal is to identify effective disease-modifying therapeutic strategies for CP**. Chronic inhibition of pancreatic prostaglandin E₂ (PGE₂) production is one such promising strategy. Indomethacin (IN) is an inhibitor of COX-2 and suppresses systemic PGE₂ production, but the pharmacology of IN in human pancreas is unknown. This study will determine whether a standard clinical oral dose of IN, administered for 4 weeks, decreases PGE₂ concentrations in pancreatic juice, setting the stage for a subsequent large-scale clinical trial of IN in CP.

PGE₂ is produced at sites of inflammation by the cyclooxygenase-2 enzyme (COX-2), which is overexpressed in the pancreas of humans with CP. PGE₂ is a potent mediator of pancreatic chronic inflammation and stellate cell activity. Pancreas juice (PJ) PGE₂ concentrations are elevated in patients with CP and suspected early or “minimal change” CP (MCCP) compared to normal volunteers. PJ can be collected during GI endoscopy and subsequently assayed for PGE2, providing a minimally invasive method of assessing pancreatic COX-2 activity. Rectally administered IN prevents acute post-ERCP pancreatitis, although the mechanism by which it prevents human acute pancreatitis is uninvestigated.

Chronic inhibition of pancreatic COX-2 is a promising therapeutic strategy for CP, but there are no data regarding the drug, dose, and route of administration required for steady-state inhibition of human pancreatic COX-2 activity.

2.2 BACKGROUND

Significance

There is currently no medical therapy that alters the natural history of chronic pancreatitis (CP). CP is a chronic disease marked by pancreatic inflammation, fibrosis, and acinar loss, with clinical manifestations including chronic pain, bouts of acute pancreatitis, and loss of pancreatic function. CP is typically diagnosed on the basis of changes in pancreatic morphology apparent on imaging studies, and/or by demonstration of loss of pancreatic exocrine function.³ The prevalence of CP is approximately 50 per 100,000 persons, or about 150,000 to 200,000 Americans, with about 15,000 to 20,000 new cases diagnosed annually in the United States.⁴ CP often affects young adults in the prime of life, and is associated with profound disability and impairment of quality of life due to chronic pain and complications of pancreatic insufficiency.⁵

[figure not shown]
COX-2 inhibition may modify symptoms and retard progression of CP. Induction of the cyclooxygenase 2 (COX-2) enzyme leads to production of thromboxanes and prostaglandins, including prostaglandin E2 (PGE₂), a potent mediator of inflammation. PGE₂ is a potent mediator of chronic inflammation and stellate cell activity in the pancreas, as shown in **Figure 1**. COX-2 activity is increased in human chronic pancreatitis tissue.^{6, 7} In normal human pancreas COX-2 expression is limited to islets, but in both early-stage and advanced CP COX-2 is also expressed in human acinar and ductal cells.^{6, 7} In rat models of pancreatitis propagation of pancreatic inflammation is COX-2 dependent,¹ and COX-2 inhibition lessens the severity of CCK-octapeptide-induced acute pancreatitis.⁸ In WBN/Kob rats who spontaneously develop CP, administration of rofecoxib (a selective COX-2 inhibitor) resulted in lower tissue PGE₂ levels and inhibition of pancreatic inflammation and fibrosis,⁹ however COX-2 knockout mice develop similar cerulean-induced chronic pancreatitis as wild-type mice.¹⁰ Sulindac attenuates inflammation and fibrosis in a mouse model of chronic pancreatitis,¹¹ and a COX-2 inhibitor blocked response of

activated pancreatic stellate cells to proinflammatory cytokines in an in-vitro study.¹² The role of PGE₂ in pancreatic inflammation and fibrosis may vary both with the species and the mechanism of pancreatic injury.

Although current treatment guidelines advocate short-term NSAID administration as first-line therapy for pancreatic pain,¹³ the possibility that chronic daily NSAID administration might alter the course of human CP is uninvestigated. A single 100 mg dose of rectal IN prevents post-ERCP pancreatitis in humans,¹⁴ and prophylactic rectal IN is commonly administered for this indication. However the pancreatic mechanism of action of rectal IN for prevention of post-ERCP pancreatitis has not been investigated in humans. No pharmacological data are available regarding COX-2 inhibition by nonsteroidal anti-inflammatory drugs (NSAIDS) or aspirin (ASA) in human pancreas.

Although rectal indomethacin decreases the incidence of post-ERCP pancreatitis,¹⁴ oral administration may be more appropriate for long-term treatment. For prevention of post-ERCP pancreatitis, rectal NSAID administration appears to be more effective than oral administration,¹⁵ however rectal IN administration results in earlier but lower peak plasma concentrations with evidence of incomplete absorption when compared to oral administration.¹⁵ Blood IN undergoes biliary recycling, resulting in high portal venous drug levels.¹⁵ While the early peak plasma concentration may in part account for the superior prophylactic efficacy of single-dose rectal IN when compared to oral administration, long-term rectal administration is unlikely to offer significant pharmacokinetic benefits when compared to oral administration, and compliance will likely be better with oral medication. Daily NSAID dosing is required to maintain suppression of COX-2, and transient rebound above baseline may occur when treatment is stopped.¹⁶

Pancreatic COX-2 activity can be assessed by measuring PGE₂ in pancreas juice collected during routine upper endoscopy. Patients with known or suspected CP may undergo an endoscopic pancreatic function test (ePFT). During ePFT secretin is administered intravenously, causing secretion of pancreatic juice (PJ) into the duodenum. The secreted PJ is suctioned from the duodenum via an endoscope and collected in timed aliquots, which are assayed for bicarbonate concentration (a measure of pancreatic exocrine function). PJ aliquots collected during ePFT can be assayed for PGE₂, providing an assessment of pancreatic COX-2 activity. We will also assay saliva and blood PGE₂ levels to generate pilot data regarding their correlation

[figure not shown]

with PJ PGE₂ levels; if correlation is high it may be possible to use these non-invasive biospecimens as surrogates for pancreatic juice in future studies.

Preliminary Data: We measured pancreas juice (PJ) PGE₂ levels in patients with CP (n=10), minimal change CP (MCCP) (n=25), and normal volunteers (n=10).¹⁷ There were statistically significant elevations of PJ PGE₂ in both MCCP and CP compared to normal volunteers (**Figure 2**). PJ PGE₂ (at a cutoff of 300 pg/ml) had a diagnostic accuracy of 92% for MCCP, compared to 62% for PJ bicarbonate concentration (at a cutoff of 80 mEq/L). These findings suggest that PJ PGE₂ levels may serve as a biomarker for pancreatic inflammation.

Rationale for study drug dosage:

There is no published data on the effect of IN on human pancreatic COX-2 activity. Usual clinical doses of oral indomethacin are 25-50 mg BID to TID. This study's dose of oral IN was chosen based on standard clinical dosing, published literature showing that similar blood levels are achieved with oral vs rectal administration, and the fact that steady-state administration of IN 50 mg BID orally should result in higher blood and tissue drug levels than 100 mg administered rectally once. Common side effects of IN such as dyspepsia are often dose related. Five doses of drug are required to achieve pharmacological steady state.

NIH-sponsored CPDPC Consortium: This protocol leverages resources of the NIH-funded, U01 Chronic Pancreatitis, Diabetes, and Pancreatic Cancer (CPDPC) Consortium. An overriding objective of CPDPC is “to encourage translational research focusing upon elucidating the pathogenesis that will provide a basis for understanding the natural history and developing means of diagnosis, treatment and clinical management of chronic pancreatitis”. Mayo Clinic Rochester ([name] – PI) and Ohio State University ([name] – co-PI) are members of the CPDPC, which funds principal investigator and study staff time at these institutions, providing a unique collaborative infrastructure for the proposed trial.

Impact of Study Findings: This trial will provide physiologic and pharmacologic rationale, and pilot patient-reported outcomes data, key to the design of subsequent studies of longer-term, daily IN administration to patients with CP. Such studies cannot be properly designed or funded without the data the current protocol will provide. Identification of a disease-modifying medical treatment for CP will be a major clinical advance impacting the health of persons everywhere who suffer from this disabling chronic illness.

